8.2 Clinical Global Impressions - Improvement (CGI-I)

The CGI-I is a 7-point scale that requires the clinician to assess how much the patient’s illness has improved or worsened relative to a baseline state at the beginning of the intervention. This is rated as: 1 = very much improved; 2 = much improved; 3 = minimally improved; 4 = no change; 5 =

minimally worse; 6 = much worse; or 7 = very much worse.

The CGI-I score will be summarized on both a categorical scale and a numerical scale by visit.

8.3 Caregiver Global Impression of Severity (CGI-S)

The CGI-S is a 7-point scale that requires the clinician to rate the severity of the patient's illness at the time of assessment, relative to the clinician's experience with patients who have the same diagnosis. Considering total clinical experience, a patient will be assessed on severity of illness at the time of rating. This is rated as: 1 = normal, not at all ill; 2 = borderline ill; 3 = mildly ill; 4 = moderately ill; 5 = markedly ill; 6 = severely ill; or 7 = extremely ill.

CGI-S scores and their change from baseline (RCT baseline and OLE baseline) will be summarized by treatment and visit. Frequency table will be created for CGI-S categories by treatment and visit.

8.4 9-items Motor Behavioral Assessment (MBA-9)

The MBA-9 scale is completed by the investigator and addresses core symptoms of RTT. MBA-9 was derived from the full MBA scale (37 RTT symptoms) by selecting the items that are deemed to be amenable to change and that reflect areas of meaningful clinical change. The severity of current symptoms is rated on a 5-point numerical scale; 0 = normal or never; 1 = mild or rare; 2 = moderate or occasional; 3 = marked or frequent; 4 = very severe or constant. The MBA-9 score is calculated by summing the scores of the individual items. The maximum score is 36 and higher scores represent greater severity.

MBA-9 scores and their change from baseline (RCT baseline and OLE baseline) will be summarized by visit.

8.4.1 Children's Sleep Habit Questionnaire (CSHQ)

The CSHQ includes a total sleep disturbance score and 8 sleep subscales: bedtime resistance, sleep onset delay, sleep duration, sleep anxiety, night wakings, parasomnias, sleep disordered breathing and daytime sleepiness. The items included in each subscale are presented in [Table 5](#).

Table 4 CSHQ Subscales

Subscale	Items Included
Bedtime resistance	1*, 3*, 4, 5, 6, 8
Sleep onset delay	2*
Sleep duration	9, 10*, 11*
Sleep anxiety	5, 7, 8, 21
Night wakings	16, 24, 25
Parasomnias	12, 13, 14, 15, 17, 22, 23
Sleep disordered breathing	18, 19, 20
Daytime sleepiness	26*, 27, 28, 29, 30, 31, 32, 33

* These items are to be reverse scored.

The responses to each item of the CSHQ are to be scored as Usually=3, Sometimes=2, Rarely=1, except for the items marked with * in [Table 5](#), which are considered to be “desirable” sleep behaviors and are therefore reverse scored. Items 32 and 33 are scored 1 for “not sleepy”, 2 for

“very sleepy”, 3 for “falls asleep”.

CSHQ scores and CSHQ subscale scores along with their change from baseline (RCT baseline and OLE baseline) will be summarized by visit.

8.5 Exploratory Efficacy Endpoints

8.5.1 Caregiver Quality of Life Questionnaire

The caregiver’s health-related quality of life will be assessed using the 36-item short form (SF-36). The SF-36 measures 8 domains of health-related quality of life: 1) limitations in physical activities because of health problems; 2) limitations in social activities because of physical or emotional problems; 3) limitations in usual role activities because of physical health problems; 4) bodily pain; 5) general mental health (psychosocial distress and well-being); 6) limitations in usual role activities because of emotional problems; 7) vitality (energy and fatigue); and 8) general health perceptions. These domains are used to calculate 2 composite scores, the physical health composite score (PCS) and the mental health composite score (MCS).

The items included in each subscale are presented in [Table 6](#).

Table 5 SF-36 Subscales

Subscale	Items Included
Physical functioning	3 (a to j)
Role-physical	4 (a to d)
Bodily pain	7 and 8
General health	1 and 11 (a to d)
Vitality	9 (a, e, g and i)
Social functioning	6 and 10
Role-emotional	5 (a to c)
Mental health	9 (b, c, d, f and h)

The raw SF-36 data will be sent to Optum via Rave Web Services so that the subscales and composite scales can be scored by the QualityMetric Health Outcomes™ Scoring Software 5.0. The scores will then be uploaded into the electronic database.

The scoring of the SF-36 questionnaire via the QualityMetric Health Outcomes™ Scoring Software 5.0 is based on norm-based scoring which ensures that the scores for the subscales have a mean of 50 and a standard deviation of 10, based on the 2009 US general population (Maruish, 2011). A higher score is indicative of a better health state.

The steps that the software follows to score the scales and composite scales are summarized below:

1. Some of the items are recoded to ensure that a higher score corresponds to a better health state for all items in the SF-36.
2. The raw scores for the health domain scales are calculated as the sum of the final response values for the items included in each scale.
3. Transform the score to a 0-100 scale score:

$$\text{Transformed scale score} = (\text{Actual raw score} - \text{Lowest possible raw score}) / \text{Possible raw score range} \times 100$$

4. Transform to z-scores \sim Normal(0,1) according to the 2009 US general population norms.
5. Calculate T scores for each domain = $T \text{ score} = 50 + (\text{domain } z\text{-score} \times 10)$. T scores calculated to aid interpretation.
6. Finally calculate MCS and PCS using a 3 step procedure:

First, the eight health domain scales are standardized using means and standard deviations from the 2009 U.S. general population. Second, these standardized scores are aggregated using weights (factor score coefficients) from the 1990 U.S. general population. Third, aggregate PCS and MCS scores are standardized using a linear *T*score transformation with a mean of 50 and a standard deviation of 10.

SF-36 composite scores and SF-36 subscale scores along with their change from baseline (RCT baseline and OLE Baseline) will be summarized by visit.

8.5.2 Patient Quality of Life Questionnaire

This instrument is a well-validated general QoL measure in pediatric populations with chronic illness. It measures QoL of the child and the family by parent or child report. The caregiver will be asked to complete the questionnaire on behalf of the patient. The CHQ-PF50 covers multidimensional health concepts including Physical Functioning, Role/Social Limitations–Emotional/Behavioral, Role/Social Limitations– Physical, Behavior, Mental Health, Self-Esteem, General Health , Bodily Pain, Family Activities, Parent Impact–Time, Parent Impact–Emotional, and Family Cohesion. Scores for specific items and subscales, as well as a standardized physical summary (PhS) score and a standardized psychosocial summary (PsS) score, can be calculated from the CHQ-PF50 questionnaire. Scores are based on a 0 to 100 scale and higher scores indicate better quality of life.

Table 7 presents the items included in each health concept.

Table 6 CHQ-PF50 Health Concepts

Health Concept	Items Included
Global health item	1.1
Physical functioning	2.1 (a to f)
Role/social limitations due to emotional/behavioral difficulties	3.1 (a to c)
Role/social limitations due to physical health	3.2 (a to b)
Bodily pain and discomfort	4.1 and 4.2
Behavior	5.1 (a to e) and 5.2
Global behavior item	5.2
Mental health	6.1 (a to e)
Self esteem	7.1 (a to f)
General health perceptions	8.1 (a to e) and 1.1
Change in health item	8.2
Emotional impact on parent	9.1 (a to c)
Time impact on parent	9.2 (a to c)
Family activities	9.3 (a to f)
Family cohesion item	9.4

Details regarding the scoring of the health concepts of CHQ-PF50 and of the PhS and PsS can be found in [Appendix 5](#). All of the health concepts and scales included in CHQ-PF50, except for the

change in health item are continuous.

CHQ-PF50 standardized scores (as per [Appendix 5](#)) CHQ-PF50 subscale scores, PhS and PsS scores along with their change from baseline (RCT Baseline and OLE Baseline) will be summarized by visit.

8.5.3 Hospital Services Use Questionnaire

The Hospital Services Use Questionnaire captures the frequency of hospital visits and patient hospitalizations. The responses to this questionnaire will be listed only.

8.5.4 Caregiver Assessment of Rett Symptoms

The Caregiver Assessment of Rett Symptoms is a symptom diary, including 12 items, each scored between 0 and 10, where a higher score for all items except items 1 and 9 represents a greater severity. Items 1 and 9 will be reverse-scored and a total score will be calculated as the sum of items 1 to 10, 11a and 12a. For items 11 and 12, if 11 is 'No' then 11a should be scored 10 and if 12 is 'No' then 12a should be scored 0. A visit score will be derived for each item and for the total score as the mean of the scores since the previous visit.

The total scores and the scores for each item of the Caregiver Assessment of Rett Symptoms along with change from baseline (RCT baseline and OLE baseline) will be summarized by visit.

9. Safety and Tolerability Analysis

9.1 Adverse Events

All reported AEs will be classified by system organ class (SOC), and preferred term (PT) and lower level term using Version 21.1 of MedDRA or higher.

The following summaries will be generated (counts are by patient unless specified otherwise):

Overall summary of TEAEs, including following description:

- Summary of TEAEs.
- Summary of treatment-related TEAEs.
- Summary of TEAEs leading to permanent discontinuation of IMP.
- Summary of serious TEAEs.
- Summary of treatment-related serious TEAEs.

Following summaries will be presented by SOC and PT:

- Summary of TEAEs
- Summary of treatment-related TEAEs
- Summary of TEAEs by maximal severity.
- Summary of serious TEAEs
- Summary of non-serious TEAEs.
- Summary of treatment-related serious TEAEs.
- Summary of TEAEs leading to permanent discontinuation of IMP.
- Summary of treatment-related TEAEs leading to permanent discontinuation of IMP.

- Summary of TEAEs leading to IMP dose reduction excluding permanent discontinuation (by resolution and overall).
- Summary of treatment-related TEAEs leading to IMP dose reduction excluding permanent discontinuation (by resolution and overall).
- Summary of TEAEs leading to IMP interrupted (by resolution and overall).
- Summary of treatment-related TEAEs leading to IMP interrupted (by resolution and overall).
- Summary of fatal TEAEs.
- Summary of TEAEs by time of first onset of AE.
- Summary of TEAEs by time to AE resolution.
- Summary of TEAEs reported in $\geq 2\%$ of patients (after rounding)
- List of patients experiencing TEAEs by SOC and preferred term.

For the summary of TEAEs by maximal severity, for each patient, the worst severity recorded by PT, SOC and overall will be used for summary purposes. If severity is missing, the worst case (severe) will be assumed.

For summaries by resolution, AEs with an outcome of ‘recovered’ or ‘recovered with sequelae’ will be summarized as ‘Resolved’ and AEs with an outcome of ‘continuing’, ‘patient died’ or those with a missing outcome will be summarized as ‘Not resolved’.

For the summary of TEAEs by time of first onset of AE, data will be summarized under the following categories:

- Month 1 (Day 1–29).
- Month 2 (Day 30–59).
- Month 3 (Day 60–89).
- Month 4-6 (Day 90–179).
- Month 7-9 (Day 180–269).
- Month 10-12 (Day 270–359).
- >1 year (> Day 359).

If patients have multiple occurrences of an AE then the AE will be counted once for the first occurrence only. Percentages will be based on the number of patients in the safety analysis set who have a visit or follow-up call within each time period above. In case there is no planned visits in the interval, percentages will be based on the number of patients in the safety analysis set.

For the summary of TEAEs by time to AE resolution, data will be summarized under the following categories:

- 1 week (≤ 7 days).
- 2 weeks (8–14 days).
- 3 weeks (15–21 days).
- 4 weeks (22–28 days).
- >4 weeks (>28 days).
- Ongoing (for AEs not resolved).

If patients have multiple occurrences of an AE then the AE will be counted once for the occurrence with the longest time to AE resolution. However, if any of the AEs are not resolved then the AE will be counted once within the ‘Ongoing’ category.

The start and stop day of the AE relative to Day 1 will be calculated as per [Section 6.1.4](#).

All TEAEs will be listed. Listings will include the start and stop day of the AE, and limited demographic information about the patient (age, sex, race and weight at screening). A separate listing will be provided for serious AEs and events of special interest (see [APPENDIX](#)).

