12.6 Reporting Procedures for All Adverse Events

All AEs (including SAEs) occurring during the trial will be reported on the running logs in the AE section of the eCRF. This includes all events from the time following screening (Visit 1) up to and including the post-trial safety follow-up visit (Visit 16), whether or not attributed to GWP42003-P and observed by the investigator or patient.

For the patient's expected seizure types, these do not routinely require documentation as AEs. However, any worsening, including a change in the pattern or severity of seizures, should be documented in the CRF if deemed to meet the definition of an AE, in the investigator's opinion.

Any AE that meets the SAE criteria should still be reported as an SAE.

The following information will need to be provided for all AEs:

A) Adverse Event (Diagnosis or Syndrome, if Known, or Signs and Symptoms)

Where the investigator cannot determine a diagnosis, signs or symptoms should be recorded in the AE section of the eCRF. Once a diagnosis has been determined, the AE section of the eCRF must be updated to reflect the diagnosis in replacement of the original symptoms. In circumstances where only a provisional diagnosis is possible (working diagnosis), the eCRF must be updated to reflect the provisional diagnosis in replacement of the original symptoms. In some circumstances, it may be relevant for the investigator to include the symptoms alongside the diagnosis in the verbatim event

Study Code: GWND19002
EudraCT Number: 2019-001605-24
Clinical Protocol V2 18Dec19

description. However, the diagnosis (full or provisional) should be clearly stated, e.g., fever and malaise due to respiratory tract infection.

B) Adverse Event Start Date and Stop Date

The start and stop dates of the event must be provided. All AEs require these fields to be completed in full. Partial dates or missing dates are not normally acceptable, and significant effort must be undertaken to obtain any unknown information. If a precise date is not known, an estimated date should be provided instead. When a complete date cannot be given, record as much information as possible (i.e., the month and year or, in exceptional circumstances, just the year). When the actual start date becomes known, the eCRF must be updated to replace the previously recorded date.

C) Outcome

The outcome of the event must be recorded accurately and classified into one of the following categories:

- Recovered
- Recovered with sequelae

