6.1.6.1.3 Adverse Events

Missing and/or incomplete dates for AEs will be imputed in a manner resulting in the earliest onset or the longest duration during the treatment period, while ensuring that the start date is not after the stop date, i.e. missing start dates will be imputed as the first day of the month/first month of the year and missing stop dates will be imputed as the last day of the month/last day of the year, while ensuring that the start date is not after the stop date. Upper and lower limits of imputation will be date of Visit 1 and last visit date as defined in [section 6.1.3](#), and events occurring on date of Visit 1 will be assumed post-IMP. Stop dates will not be imputed if the AE is ongoing.

Imputed dates will be used for calculation of time to first onset and time to AE resolution, they will not be presented in AE listings.

A worst-case approach will be followed in the event of missing severity or causality data. If the

severity is missing, 'Severe' will be imputed. If causality data is missing for a treatment emergent AE (TEAE), 'Yes' will be imputed for the question 'Plausible relationship to study medication'.

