6.1.8.1 Adverse events

Any adverse events occurring between last dose of RCT and OLE visit 1 will not be considered Treatment Emergent Adverse events (Aes occurring during study break). All other adverse events will be considered as treatment-emergent adverse events.

A TEAE will be considered treatment-related if the plausibility relationship to IMP is recorded on the eCRF as 'yes'. If the data on plausibility relationship to IMP is missing then the TEAE will be considered treatment-related.

A TEAE will be considered leading to permanent discontinuation of IMP (leading to withdrawal) if the action taken with IMP is recorded on the eCRF as 'trial medication stopped' or the outcome is recorded on the eCRF as 'patient died'.

A treatment-related TEAEs leading to withdrawal is a TEAE leading to permanent IMP discontinuation and considered treatment-related as per above definition.

A TEAE will be considered leading to IMP temporary discontinuation if the action taken with IMP is recorded on the eCRF as 'trial medication interrupted'.

A TEAE will be considered leading to permanent IMP dose reduction excluding permanent discontinuation if the action taken with IMP is recorded on the eCRF as 'dose reduced'.

A TEAE will be considered fatal if the outcome is recorded on the eCRF as 'patient died'.

The time to first onset of AE will be calculated for TEAEs as:

$$\text{Start date of AE} - \text{Day 1} + 1$$

The time to AE resolution will be calculated for TEAEs as:

$$\text{Stop date of AE} - \text{Start date of AE} + 1$$

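### In the time-to-AE-resolution table, the Ongoing row also counts fatal AEs and AEs that have a stop date but no recorded outcome

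*SAP*

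**What the plan says.** Protocol V2 section 12.6 requires each AE to have an outcome: "The outcome of the event must be recorded accurately and classified into one of the following categories". There are four codes: recovered, recovered with sequelae, continuing, and patient died. Continuing and death are therefore collected separately.

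SAP 9.1 reduces these codes to two classes. The sentence begins "For summaries by resolution, AEs with an outcome of" recovery, with or without sequelae, and calls those events resolved. The rest follow this rule: "AEs with an outcome of ‘continuing’, ‘patient died’ or those with a missing outcome will be summarized as ‘Not resolved". Four summaries carry the by-resolution label: dose reduction and treatment interruption, each for all TEAEs and for treatment-related TEAEs.

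The time-to-resolution table is listed separately in SAP 9.1. It has bands for 1, 2, 3, 4 and more than 4 weeks, and a final row "Ongoing (for AEs not resolved". For a patient with several occurrences of the same AE, "if any of the AEs are not resolved then the AE will be counted once within the ‘Ongoing’ category".

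SAP 6.1.8.1 introduces the duration formula with "The time to AE resolution will be calculated for TEAEs as" and gives stop date minus start date plus 1, with no condition on outcome. SAP 6.1.6.1.3 imputes missing or incomplete stop dates for this calculation, except that "Stop dates will not be imputed if the AE is ongoing". It does not say there what makes an AE ongoing.

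**The concern.** AEs come first in the list of primary safety endpoints, and the trial is purely descriptive, so the AE tables are its main output. A reader who wants to know how often harm persists on long-term treatment will look at the Ongoing row. As the rules stand, that row mixes three situations: events that were still present, events that ended in death, and events whose outcome field was left blank. A death is not a continuing event. A blank outcome beside a recorded stop date points to a gap in data entry more than to persistence. Because one unresolved occurrence overrides the patient's resolved occurrences of the same AE, a single blank field can also move a patient out of a duration band.

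**Working it through.** The plan states no figure on this point, so the check follows each outcome code through the rules.

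| Recorded outcome | Recorded stop date | Class (SAP 9.1) | Row in the time-to-resolution table |
|---|---|---|---|
| Recovered, with or without sequelae | yes | Resolved | Duration band |
| Continuing | no | Not resolved | Ongoing |
| Patient died | yes or no | Not resolved | Ongoing |
| Missing | yes | Not resolved | Ongoing |
| Missing | no | Not resolved | Ongoing |

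The third and fourth lines are the problem.

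**Worked case, with assumed days.** An AE starts on Day 100, stops on Day 105 and has no outcome recorded. The formula in SAP 6.1.8.1 gives 105 − 100 + 1 = 6 days, which is the 1-week band. The outcome rule in SAP 9.1 puts the same event in Ongoing.

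**Alternative reading.** Suppose Ongoing means only that no stop date exists. The blank-outcome event above then falls in the 1-week band, as the formula says. But a fatal AE with a stop date also falls in a duration band and appears to have resolved. Under neither reading does the table have a correct place for a death.

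**Missing outcome and no stop date.** One programmer could impute a stop date under SAP 6.1.6.1.3 and assign a duration band. Another could treat the event as ongoing, impute nothing and leave it in the last row. The text supports both.

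**Size.** If n patients are counted in Ongoing for a given term, and k of them are there only because of a death or a blank outcome beside a stop date, the share that does not belong is k/n. The documents give neither number. With n = 10 as an assumption, k = 0, 1 or 3 gives 0%, 10% or 30%. This shows how the share behaves in a small row. It is not an estimate.

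**The case against.** **The definition is worded for other tables.** It opens by limiting itself to summaries by resolution, and the time-to-resolution table is specified separately. This stands as a caveat. However, it is the only definition of not resolved in the SAP and sits in the same section, and the alternative reading does not place deaths correctly either.

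**Deaths are reported elsewhere.** SAP 9.1 lists "Summary of fatal TEAEs" by system organ class and preferred term, and all TEAEs are listed with start and stop days. This also stands. A reader might infer that the plan conceals deaths, and the documents do not support that.

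**The four by-resolution tables share the fault.** A reader might infer this because they use the same class. They do not share it. Their label is Not resolved, which is fair for a death. Under SAP 6.1.8.1 a fatal TEAE counts as leading to permanent discontinuation, so it falls outside the two dose-reduction tables, which exclude such events.

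**A blank outcome treated as unresolved is a cautious convention.** SAP 6.1.6.1.3 takes the worst case for missing severity and causality. That is defensible when nothing else is known, and an AE with neither outcome nor stop date may indeed be ongoing. So it would be too strong to say that every missing outcome is misplaced. The argument is weak where a stop date has been recorded.

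**The formula does not say that every event with a stop date has resolved.** Correct. It supplies a duration, and SAP 9.1 decides who receives one. The two sections leave a gap for blank outcomes more than they contradict each other outright. The table shells, which might carry a clarifying note, are a separate document and could not be checked.

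**Conclusion.** The point holds for one table. As written, the Ongoing row of the time-to-resolution table includes fatal AEs and AEs with a recorded stop date but no outcome, and so overstates the number of persisting events. The number is unknown and probably small, since the protocol requires an outcome for every AE. No estimate, test or count of deaths changes, because the trial is descriptive and fatal TEAEs have their own table. The conclusion rests on applying the section's single definition of not resolved to a table that uses the term without defining it. It is a minor matter of presentation, worth correcting because the codes needed are already collected.

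**What to change.** In the time-to-resolution table of SAP 9.1:

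- Limit Ongoing to events with the outcome continuing.
- Add a Fatal row for events with the outcome patient died.
- Add an Outcome missing row for events with no outcome and no recorded stop date. A date imputed under SAP 6.1.6.1.3 does not count as recorded.
- Place events with a missing outcome but a recorded stop date in the duration bands by the SAP 6.1.8.1 formula, and give their number in a footnote.
- State which row takes precedence when a patient's occurrences of one AE fall in different rows, since the present rule knows only Ongoing and the longest duration.

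Leave the four by-resolution tables as they are. The cost is a few lines of SAP text, two rows and a footnote, with no new data. The small downside is that the footnoted events are shown as ended without a recorded recovery, which is less cautious than the present rule; the footnote lets the reader judge how much that matters.

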9.1.1.2 Visit 4 (Day 29 [± 7])

A visit window of ± 7 days from the scheduled visit date is permitted, but it is preferred that the visit is performed on the scheduled visit day, where possible.

Information regarding changes to concomitant medications and AEs will be reviewed.

The investigator must assess adherence to the dosing schedule.

Vital sign assessments, physical examination (including body weight) and ECG assessments will be performed.

Clinical laboratory samples (urine [where possible] and blood) will be taken for hematology and biochemistry.

The caregiver will complete the RSBQ and Caregiver Assessment of Rett Symptoms.

The Hospital Services Use Questionnaire will be completed via interview.

The investigator will complete the CGI-S, CGI-I, and suicidality assessment.

All GWP42003-P (used and unused) will be collected, and a check of the returned GWP42003-P against usage should be made. Patients will receive sufficient GWP42003-P and a dosing schedule for the following 4 weeks.

Based on [Section 9.1.3](#), assessments may be performed at an unscheduled visit in the event of a safety concern, as deemed necessary by the investigator.

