9.1.1.3 Visit 5 (Day 57 [± 7])

A visit window of ± 7 days from the scheduled visit date is permitted, but it is preferred that the visit is performed on the scheduled visit day, where possible.

Information regarding changes to concomitant medications and AEs will be reviewed.

The investigator must assess adherence to the dosing schedule.

Vital sign assessments will be performed.

Clinical laboratory samples (urine [where possible] and blood) will be taken for hematology and biochemistry.

The caregiver will complete the RSBQ and Caregiver Assessment of Rett Symptoms.

Study Code: GWND19002
EudraCT Number: 2019-001605-24
Clinical Protocol V2 18Dec19

The Hospital Services Use Questionnaire will be conducted via interview.

The investigator will complete CGI-S, CGI-I, and suicidality assessment.

All GWP42003-P (used and unused) will be collected, and a check of the returned GWP42003-P against usage should be made. Patients will receive sufficient GWP42003-P and a dosing schedule for the following 4 weeks.

Based on [Section 9.1.3](#), assessments may be performed at an unscheduled visit in the event of a safety concern, as deemed necessary by the investigator.

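### The time-of-onset adverse event table divides by patients who had a visit or call in the interval, a group that is neither the patients under observation nor certain to contain the numerator

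*SAP*

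**What the plan says.** SAP section 9.1 sorts first onsets into seven intervals: Days 1–29, 30–59, 60–89, 90–179, 180–269, 270–359 and beyond Day 359.

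- **Numerator:** "If patients have multiple occurrences of an AE then the AE will be counted once for the first occurrence only". Nothing requires the patient to have had a visit in that interval.
- **Denominator:** "Percentages will be based on the number of patients in the safety analysis set who have a visit or follow-up call" within the interval.
- **Fallback:** "In case there is no planned visits in the interval, percentages will be based on the number of patients in the safety analysis set".

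Protocol V2 sections 9.2.15 and 12.6 collect adverse events continuously from Visit 1 to the follow-up call at Visit 16. The schedule (Protocol V2 Appendix 1, SAP Table 1) places Visits 4, 5 and 6 at Days 29, 57 and 85, each ±7 days.

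**The concern.** A percentage of patients with an onset in a period should be taken over a group that includes everyone who could contribute an onset. Here membership of the denominator depends on when a clinic appointment fell. A patient seen on Day 29 and next on Day 60 is under observation for the whole of Month 2. An event she has on Day 45 is counted, yet she is not in the Month 2 denominator. Both visits are within their windows.

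Long-term safety is the primary objective, and this is the planned tabulation of whether events arise early or late. The effect differs by interval: Month 1 is untouched because everyone has Visit 1, while Months 2 and 3 can shift through scheduling alone. Part of an apparent time pattern could therefore be an artefact of visit timing.

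**Working it through.** The plan gives no percentage, sample size or power for this table, so there is no figure to reproduce. The documents give neither actual visit timing nor missed-visit rates, so the sizes below rest on stated assumptions.

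**1. Visits mapped to intervals.** Windows: Visit 4, Days 22–36; Visit 5, Days 50–64; Visit 6, Days 78–92; Visit 7, Days 134–148; Visit 8, Days 190–204; Visit 9, Days 274–288.

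- Month 1 contains Visit 1 for everyone.
- On nominal days, Months 2 and 3 hold only Visit 5 (Day 57) and Visit 6 (Day 85). Both windows run past the end of the interval.
- Visits 7, 8 and 9 lie wholly inside Months 4–6, 7–9 and 10–12.
- Every interval has a planned visit.

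**2. When a compliant patient drops out of a denominator.**

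- Month 2: Visit 4 by Day 29 and Visit 5 on Day 60 or later.
- Month 3: Visit 5 by Day 59 and Visit 6 on Day 90 or later.

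**3. Size, with visit days independent and uniform within ±w days.** Loss P is the product of the two probabilities. The ratio of the SAP percentage to one based on patients observed is 1/(1 − P).

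| w | Month 2 loss | Ratio | Month 3 loss | Ratio |
|---|---|---|---|---|
| 0 | 0 | 1.00 | 0 | 1.00 |
| 3 | 4/7 × 1/7 = 8.2% | 1.09 | 0 | 1.00 |
| 5 | 6/11 × 3/11 = 14.9% | 1.17 | 8/11 × 1/11 = 6.6% | 1.07 |
| 7 | 8/15 × 5/15 = 17.8% | 1.22 | 10/15 × 3/15 = 13.3% | 1.15 |

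If visits cluster on the nominal day (truncated normal, SD 2, 3 or 4 days, still independent), the losses are 6.2%, 11.2% and 13.9% in Month 2, and 1.0%, 4.9% and 7.9% in Month 3.

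Illustration with the planned 252 patients and w = 7: 17.8% of 252 is about 45, leaving 207. Ten first onsets in Month 2 give 10/207 = 4.8% under the SAP and 10/252 = 4.0% by patients observed.

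**4. Months 4–6, 7–9 and 10–12.** A loss needs a missed visit with no other visit or call in the interval. If a fraction m is lost this way, the ratio is 1/(1 − m): 1.05 for m = 5% and 1.25 for m = 20%. Both rates are assumed.

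**5. Comparison with patients still free of the event.** Assume a constant first-onset hazard h per day, no dropout, and w = 7. The share of all patients with first onset in an interval of L days that follows s earlier days is exp(−hs) × [1 − exp(−hL)]. The share among those still event-free is 1 − exp(−hL).

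| Interval | h | SAP | Event-free |
|---|---|---|---|
| Month 2 (s = 29, L = 30) | 0.001 | 2.87%/0.822 = 3.5% | 3.0% |
| Month 2 | 0.01 | 19.4%/0.822 = 23.6% | 25.9% |
| Months 7–9 (s = 179, L = 90) | 0.001 | 7.2% | 8.6% |
| Months 7–9 | 0.01 | 9.9% | 59.3% |

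The 0.822 is 1 − 0.178. Months 7–9 have no window loss. The SAP figure is above the event-free figure in the first row and below it in the other three, because patients who have already had the event stay in later denominators.

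**The case against.** The best case against the point is that the loss may be small or nil. Dropping out of Month 2 or Month 3 needs a gap of at least 31 days between consecutive visits (Day 29 to Day 60, or Day 59 to Day 90). Protocol V2 prefers the scheduled day, and Visits 4 and 5 each supply drug for the following four weeks. With a 28-day gap nobody is lost, so independent uniform windows are close to a worst case. The clustered figures share the independence assumption. A follow-up call also counts, as may an unscheduled visit, and a patient who withdraws would normally have a withdrawal visit and a follow-up call. All of this stands, and it makes the 18% and 13% upper-end values.

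Four stronger readings are tempting and are not supported:

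- **That the percentages are generally inflated.** There is no inflation in Month 1 or on the nominal schedule, and against event-free patients the figure can be too low.
- **That the fallback brings departed patients into the denominator.** It applies only where no visit is planned, and every interval has one.
- **That this is the only view of event timing.** Section 9.1 also lists every TEAE with its start and stop day, and the interval counts do not depend on the denominator.
- **That COVID-19 disruption makes the effect large.** The documents give no missed-visit rate for this trial.

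What the objection does not remove is the rule itself, under which a compliant patient can be counted above the line and not below it.

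**Conclusion.** The denominator is defined by attendance rather than observation, and it need not contain the numerator. Relative to patients observed, the overstatement runs from none to factors of about 1.22 in Month 2 and 1.15 in Month 3. The upper values assume independent, uniform visit days within ±7 days. From Month 4 to Month 12 any loss comes only from a missed visit with no other contact in the interval. Relative to patients still free of the event, the direction varies with how common the event is and how late the interval.

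The reach is limited: one descriptive table, no hypothesis test, and no effect on overall TEAE incidence. It is still worth correcting, because this table is meant to show the time pattern and the correction is small.

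**What to change.** In SAP section 9.1, define the denominator for each interval as the safety-set patients still under observation on its first day, meaning last contact on or after that day. Count the Visit 16 call as a contact: the last-visit definition in SAP section 6.1.3 stops at Visit 15, while events are collected to Visit 16. All patients start at Day 1 and an event can be recorded only up to last contact, so this group contains the numerator by construction. Membership also then depends on dates, not on the eCRF visit label under which a withdrawal visit is stored.

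If a percentage among patients at risk of first onset is wanted, also exclude those with a prior onset of that event, and say so in the table title. Delete the fallback to the whole safety set, which is not triggered on the planned schedule and becomes unnecessary.

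The cost is one SAP sentence and a small change to the denominator code, using dates already collected.
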